proposed that the estimation of the application of MEESSI-AHF should always be adjusted by center and professional in charge of the patient. More exhaustive details of the analysis procedures for the three studies will be reflected in a Statistical Analysis Plan (SAP) agreed with the PI of the project before the closure of the different databases. It will describe in detail both the main analysis population criteria for each study and the statistical analysis of the data. Likewise, the strategy for handling missing data or loss to follow-up of patients will be elaborated.

We would like to point out that the paradigm on which the non-observational part of this research focuses, the use of MEESSI-AHF as an aid in the decision to discharge/admit patients with AHF to the ED, has non-trivial weaknesses. In the case of Study 2, the fact that the two groups (usual clinical practice, pre-phase; and use of the MEESSI-AHF scale; post phase) are not contemporaneous could have an impact on cohort bias, since part of the differences could be due to the temporal effect in the inclusion of patients. In the case of the randomized experimental design, Study 3, the main bias may come from contamination between groups. Given that the patients will be randomized, it is possible that, due to experience of use, there may be professionals who intuit the result that could occur with the MEESSI-AHF scale in patients randomized to routine clinical practice and make the discharge/admission decision in this group with a certain influence of the intervention under study (use of the risk stratification tool). It is therefore proposed that the positive conclusion of the implementation of the MEESSI-AHF scale should be based on obtaining positive results simultaneously in Studies 2 and 3. If not, a post-hoc evaluation of the studies will be necessary to assess possible biases and the impact on the results.

The main termination rule for Study 3, of longer duration than Study 2, would be that in the analysis of PRV-2, which is done at 30 days, a significantly worse evolution is observed in patients in the IG compared to the CG. For this procedure, a specific working group will be created, which will be made up of independent professionals.

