Stage 7: Entry of the data from Study 2 (post phase) into the database, and first analysis (corresponding to the short-term results, 30 days) of the objectives set in Study 2. Time required: 6 months (from month 13 to month 18).

Stage 8: Study of the status of Study 2 patients (post phase) at one year after the index event (emergency room visit). Time required: 2 months, 12 months after the end of Stage 6 (months 25 and 26).

Stage 9: Entry of the remaining data from Study 2 into the database, final analysis of the objectives set in Study 2 (including long-term results). Communication of results. Time required: 4 months (months 27 to 30).

Stage 10: Preparation of the emergency professionals of the 10 centers participating in Study 3 (clinical trial), with training in the use of the risk stratification calculator using the MEESSI-AHF scale. Review of the inclusion and exclusion protocol, randomization procedure, and allocation arms. Time required: 3 months (month 7 to month 9).

Stage 11: Inclusion of patients in Study 3. It is planned to randomize 1-2 patients per center per day (1.5 on average), until reaching the total N (4,054 patients; 2,027 per arm). Time required: 9 months (month 10 to month 18).

Stage 12: Entry of Study 3 data into the database, and first analysis (corresponding to short-term results, 30 days) of the objectives set in Study 3. Time required: 6 months (month 19 to month 24).

Stage 13: Study of the status of Study 3 patients (post phase) one year after the index event (emergency department visit). Time required: 2 months, 12 months after the end of Stage 11 (months 31 and 32).

Stage 14: Entry of the remaining data from Study 3 into the database, final analysis of the objectives set out in Study 2 (including long-term results). Communication of results. Time required: 4 months (months 33 to 36).

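### Study 3's harm-termination rule has no scheduled look during enrolment: data entry and the first 30-day analysis come after all 4,054 patients are due to be randomised

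*Combined protocol and SAP*

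**What the plan says.** The rule stands at the end of the Study 3 text on data collection and analysis. It names the outcome first: "The main termination rule for Study 3, of longer duration than Study 2, would be that in the analysis of PRV-2". The trigger for stopping is then given in these words: "which is done at 30 days, a significantly worse evolution is observed in patients in the IG compared to the CG". On who applies it, the text says: "For this procedure, a specific working group will be created, which will be made up of independent professionals". No date, patient count, number of looks or significance level is attached.

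PRV-2 (called PROM-2 under Study 2, Variables) is the composite of ED revisit, hospitalisation or death within 30 days of discharge, in patients sent home directly from the ED. Study 3 takes over the Study 2 outcomes.

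Further analysis detail is deferred to a SAP "agreed with the PI of the project before the closure of the different databases". On its contents: "It will describe in detail both the main analysis population criteria for each study and the statistical analysis of the data"; a strategy for missing data and losses to follow-up is added. Interim review is not named.

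In the work plan, Stage 11 sets the pace of enrolment: "It is planned to randomize 1-2 patients per center per day (1.5 on average), until reaching the total N", which is 4,054 patients (2,027 per arm), over nine months from month 10 to month 18. Stage 12, in months 19-24, is: "Entry of Study 3 data into the database, and first analysis (corresponding to short-term results, 30 days) of the objectives set in Study 3". The remaining Study 3 stages are the one-year status check (months 31-32) and the final analysis (months 33-36).

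**The concern.** A rule for ending a trial because of harm limits exposure only if someone can apply it while patients are still being randomised. Here the outcome matures quickly, in 30 days, but the work plan does not enter the data until recruitment is due to be complete. A harmful effect of the tool on discharged patients could be visible in outcomes that have already occurred, yet no planned step would put those outcomes before the independent group in time.

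This is the only termination rule stated for Study 3, and the gap must be closed before enrolment starts. A SAP agreed just before database closure would come too late to arrange looks during months 10-18.

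**Working it through.** **Inputs.** 10 EDs, 1:1 allocation (Study 3, Design); 1-2 patients per centre per day, 1.5 on average, N = 4,054, months 10-18 (Stage 11); data entry and first 30-day analysis in months 19-24 (Stage 12); 30% discharged directly, PRV-2 rate 25%, planned effect 25% to 18% (sample size calculation).

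**1. The plan's enrolment period.** 10 × 1.5 = 15 per day; 4,054 / 15 = 270 days, about 9 months. The stated duration is reproduced. Stage 12 opens in month 19, so on the planned schedule no patient remains to be randomised.

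**2. What would already be known.** By day 270, patients enrolled up to day 240 have reached 30 days: 15 × 240 = 3,600, and 3,600 / 4,054 = 89%. This takes the 30-day clock as starting at about enrolment. Timely looks were feasible.

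**3. Accrual range.** At 1 per centre per day, enrolment takes 4,054 / 10 = 405 days, and 4,054 − 10 × 270 = 1,354 patients remain at day 270. At 2 per centre per day it takes 4,054 / 20 = 203 days. Only slow accrual that misses the nine-month target creates an overlap with Stage 12.

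**4. Illustrative looks at one third and two thirds of 30-day data (15 per day).**

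| | Look 1 | Look 2 |
|---|---|---|
| Patients with 30-day data | 1,351 | 2,703 |
| Day | 1,351/15 + 30 = 120 | 2,703/15 + 30 = 210 |
| Still to randomise, no lag | 4,054 − 15 × 120 ≈ 2,250 | 4,054 − 15 × 210 ≈ 900 |
| Same, 14-day entry lag | 2,043 | 691 |
| Same, 30-day entry lag | 1,803 | 451 |
| Discharged per arm (30%) | 203 | 405 |

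**5. False-stop chance.** With information in the ratio 1:2, the two test statistics have correlation √0.5. If there is no true difference, the one-sided chance that either exceeds 1.96 is 4.2%, against 2.5% for a single look. A common critical value of 2.178 brings it back to 2.5%.

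**6. Chance of detecting harm.** Take a rise from 25% to 32%, the mirror image of the planned seven-point fall. The expected statistic is 0.07 / √[(0.25 × 0.75 + 0.32 × 0.68)/n], which is 1.57 at n = 203 and 2.21 at n = 405 per arm.

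| Critical value | Look 1 alone | Look 2 alone | Either look |
|---|---|---|---|
| 1.96 | 35% | 60% | 64% |
| 2.178 | 27% | 51% | 55% |

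The last column uses the same correlation as step 5. The documents specify neither two looks nor these critical values.

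**The case against.** The strongest reply is that the plan is silent here and does not contradict itself. Stage 12 is the research team's own analysis of the study objectives. The termination rule belongs to a separate independent group, whose meetings need not appear in the team's work plan. A rule for terminating a study implies use before completion, the document is a grant application, and the promised SAP could set out interim looks. Calling this the main rule also leaves room for others.

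Part of this stands. Nothing bars an earlier look, and the later SAP is not prevented from describing one. A reader might infer that the rule is inoperable, or that Study 3 has no safety oversight; the documents do not support either. An independent group is promised, and the emergency physician keeps the final decision on admission or discharge.

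What does not stand is that the group could act on the schedule as written. Any look needs entered 30-day data, and Study 3 data entry itself is placed in months 19-24. The SAP deadline does not secure an earlier arrangement. Stage 7 does produce 30-day results in months 13-18, but for Study 2, which is non-randomised, runs in other EDs and is not linked to this rule.

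Two further inferences go too far. First, that a harm boundary must be adjusted for repeated looks: a harm-only stop does not raise the chance of a false claim of benefit, and adjustment makes harm harder to detect (step 6 of the working). Second, that PRV-2 is unfit for this purpose because patients enter it through a discharge decision made after randomisation: that is a separate endpoint question and does not depend on when a look takes place.

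**Conclusion.** The point holds as a scheduling gap that defeats the plan's own safeguard. At the planned average rate, the rule as scheduled cannot spare any of the 4,054 patients from randomisation, although about 89% would have 30-day outcomes by the last day of enrolment. At the lowest planned rate about 1,354 patients would remain when Stage 12 is due to start, but only because the enrolment target had been missed.

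The enrolment figures assume uniform accrual. The detection figures also assume 30% discharged in each arm; the tool is meant to influence discharge, so the actual numbers may differ between arms. The gap should be fixed before the first randomisation. It is not evidence that interim review is prohibited.

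**What to change.** Reconcile the termination rule in the Study 3 text with Stages 11 and 12 of the work plan:

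- Enter 30-day outcomes as they accrue during Stage 11.
- Schedule the working group's review of PRV-2 while patients remain to be randomised, for example when one third and two thirds have 30-day data.
- Before the first randomisation, create the group and state the number of looks, the data flow to the group and what counts as significantly worse.
- Leave to the group whether the harm criterion is adjusted for the number of looks, with the trade-off in steps 5 and 6 in front of it.
- Optionally, show the group the number discharged per arm and 30-day all-cause death from the index event by assigned arm. That outcome is already collected and covers admitted patients too.

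**Cost.** No extra patients and no new measures. Follow-up and data entry for about 450 patients per month (15 × 30) would run alongside enrolment instead of after it. The gain is bounded: with two looks, a seven-point rise would be missed more than a third of the time even without adjustment (100% − 64% = 36%).

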### **STUDY 1**

Design: Descriptive, multicenter, non-interventional, with consecutive inclusion of patients and 1-year cohort follow-up.

Study Subjects: All patients older than 14 years who consulted in the 16 participating EDs for symptoms and signs compatible with AHF following the Framingham criteria (Ho et al. Circulation 1993; 88:107-15) will be consecutively included and the diagnosis will be verified by determination of natriuretic peptides (BNP or NT-proBNP) (Ponikowski et al. Eur Heart J. 2016;37:2129-200). Failure to confirm clinical suspicion by natriuretic peptide (because it is not determined or is not above the values considered diagnostic) or if the patient presents an episode of AHF in the context of ST-segment elevation acute coronary syndrome (STEMI) will be exclusion criteria, as in most of these cases the patient is transferred to the cardiac hemodynamics unit with minimal ED intervention.

Variables: As independent variables, more than 40 variables will be collected (see appendix) that a priori can potentially be related to the clinical evolution of patients (demographics, personal history, usual chronic treatment at home, baseline functional status and in the acute episode, clinical, analytical and ECG variables of the patient on arrival at the ED, and treatment and management in the ED, including the final destination of the patient after care -discharge/admission-) that are commonly used by the group in their work (Chest 2017; 152: 821-832; JACC Heart Fail 2018; 6:52-62; Eur J Heart Failure 2017; 19:1205-1209), including those necessary for the calculation of the MEESSEI-AHF scale score and patient stratification (Ann Intern Med 2017; 167:698-705). As outcome variables will be collected: 1) cardiovascular and all-cause mortality during the 30 days and year of the index event (ED consultation); 2) ED reconsultation (without admission) for AHF 30 days post-discharge; 3) hospitalization for AHF 30 days post-discharge; 4) all-cause mortality 30 days post-discharge; 5) the combined variable of 2+3+4 30 days post-discharge, and 6) days alive and out of hospital during the 30 days after the index event. Follow-up will be by telephone call to the patient or family member and consultation of hospital and primary care medical records (informed consent will have been collected for this). The adjudication and validation of the event will be carried out

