Variables: The independent variables will be the same as in Study 1. There will be two primary outcome variables (PROMs): PROM-1) the 1-year all-cause mortality for the overall patients included in the study (regardless of their risk category); and PROM-2) the combined variable of ED revisit, hospitalization or death at 30 days post-discharge for patients discharged directly from the ED. Secondary outcome variables will be the rest of those mentioned in Study 1. In addition, as a measure of efficiency, the percentage of

patients discharged without admission before and after the intervention with the MEESSI-AHF scale will be counted.

Sample size calculation: Presented with Study 3 (see below).

Data collection and analysis: Presented with Study 3 (see below).

Study limitations: 1) center selection bias; 2) cohort bias.

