### **STUDY 3**

**Design:** Multicenter, randomized, open clinical trial, without pharmacological intervention, in which the effect of risk stratification in the ED of patients with AHF using the MEESSI-AHF scale prior to the decision to admit or discharge will be evaluated compared to standard medical practice (without risk stratification). The 10 EDs in Study 1 that do not participate in Study 2 will participate in the study, in an attempt to limit contamination, and inclusion will be competitive. Randomization will be performed at the individual level, as the low number of participating EDs and the high heterogeneity of ED organizational models and postal care circuits make this more advisable than randomization by center. Randomization will determine the formation of the two arms of the study (1:1): patients assigned to "usual medical practice" (control group, CG) and those assigned to "risk stratification" (intervention group, IG), which will be done by means of a list provided to each center. The training of emergency professionals and the decision proposal provided by the MEESSI-AHF scale will be the same as in Study 2. The final decision on admission or discharge will depend, as in Study 2, on the emergency physician in charge of the patient, and if this decision differs from that proposed by the stratification, the reason will be stated (the same as in Study 2).

**Study subjects:** All patients diagnosed with AHF in the ED and who meet the inclusion and exclusion criteria mentioned in Study 1 will be eligible.

**Variables:** The independent variables will be the same as in Study 1 with the addition of the center and professional variables. The primary and secondary outcome variables will also be the same as in Study 2.

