**Sample size calculation (common with Study 2):** Since the objectives of assessing the effect of the MEESSI-AHF scale on the clinical course of AHF patients in Studies 2 and 3 are the same, the necessary evaluable sample size calculation is the same for both studies, and the principles used are discussed below. On the one hand, the rate of VPR-1 in our setting is around 30% (Llorens et al. *Emergencias*. 2015; 27:11-22). On the other hand, patients discharged from the ED account for 30% of AHFs seen in the ED, and it is estimated that 25% of them will present the event defined by PRV-2. We intend to show that the use of the MEESSI-AHF classification could have a significant impact on a decrease in both PRVs. The 6 centers of Study 2 could assess about 2000 patients in each of the phases of the development of this project. Thus, with 2027 patients, a decrease in 1-year mortality (PRV-1) from 30% to 26% could be seen as statistically significant. As 30% of patients with AHF seen in the ED are discharged, this represents about 600 patients. With 568 patients, a statistically significant decrease in the combined variable (PRV-2) from 25% to 18% can be assessed as statistically significant. With all this, with the inclusion of a little more than 4000 patients (Study 2: 2027 in pre-phase, 2027 in post phase; Study 3: 2027 in GI, 2027 in CG) we could achieve an assessment of a relative decrease as relevant of 13% for PRV-1 and 28% in PRV-2. Calculations were performed using a bilateral type I error of 5% and a statistical power of 80% using the nQuery Advisor program (Ver. 7.0).

**Data collection and analysis (common with Study 2):** The outcome variables in Studies 2 and 3 will be analyzed using logistic or Cox regression models, depending on whether or not it is of interest to contextualize the time of occurrence of the event studied. Specifically, in Study 2, in addition to the application of the MEESSI-AHF scale, the influence of other independent factors of interest in conjunction with the MEESSI-AHF scale will be assessed using multivariate models. In the case of Study 3, since it is a study with randomization by patient (and not stratified by center or professional), it is

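### Study 3's only stated termination rule uses PRV-2, which leaves out admitted patients; 30-day all-cause mortality in all randomised patients should be added beside it

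*Combined protocol and SAP*

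**What the plan says.** The rule stands at the end of the data collection and analysis text for Study 3. It is introduced as "The main termination rule for Study 3, of longer duration than Study 2", and it is met when "in the analysis of PRV-2, which is done at 30 days, a significantly worse evolution is observed in patients in the IG" relative to the control group. For this, "a specific working group will be created, which will be made up of independent professionals". The text gives no other termination rule, no look schedule and no significance threshold.

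PRV-2 is the second primary outcome, called PROM-2 under Study 2, Variables: "the combined variable of ED revisit, hospitalization or death at 30 days post-discharge for patients discharged directly from the ED". Study 3 takes it over: "The primary and secondary outcome variables will also be the same as in Study 2". The first primary outcome does cover everyone ("the 1-year all-cause mortality for the overall patients included in the study (regardless of their risk category"), but the termination rule does not use it.

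The sample size section gives the size of the PRV-2 group: "As 30% of patients with AHF seen in the ED are discharged, this represents about 600 patients". Outcome 1 under Study 1, Variables, which Study 3 inherits as a secondary outcome, is "cardiovascular and all-cause mortality during the 30 days and year of the index event (ED consultation"). It is not tied to termination.

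**The concern.** The intervention is a proposal to discharge or to admit. Its possible harm can fall on patients sent home or on patients kept in, and a safety rule ought to be able to see both. This rule sees only those sent home.

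Its denominator is also formed after randomisation, by the decision that the tool is meant to influence. The tool proposes discharge for low-risk patients who have improved and admission for all others. If physicians follow it, the discharged groups in the two arms differ in number and in case mix. A difference in PRV-2, or the lack of one, then mixes the effect of the tool on outcomes with its effect on who is counted. What is at stake is that Study 3 could continue, with a neutral or favourable PRV-2, while mortality across the intervention arm is higher.

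**Working it through.** **Inputs from the plan.** 2,027 per arm, 1:1 (sample size section; Work Plan, Stage 11). Discharge share 30%. PRV-2 25% in controls against 18%. PRV-1 30% against 26%. Two-sided 5%, power 80%.

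**Inputs assumed here.** Any discharge share other than 30%, event rates in additional discharges, and 30-day mortality levels. The plan gives no look schedule or threshold, so each probability below is for one look, with the rule met when the intervention arm is worse at z > 1.96.

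**Reproducing the plan's figures.** The two-proportion formula with continuity correction gives 2,027 per arm for 30% against 26%, and 568 per arm for 25% against 18%. Both match the plan.

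**Method for the rule.** With pooled proportion p̄, SE0 = √[p̄(1−p̄)(1/nI + 1/nC)] and SE1 = √[pI(1−pI)/nI + pC(1−pC)/nC]. P(rule met) = Φ[((pI−pC) − 1.96·SE0)/SE1].

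**1. Who is outside the rule.** 0.30 × 2,027 = 608 discharged per arm; 2,027 − 608 = 1,419 admitted, or 70%.

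**2. Excess deaths among admitted patients.** Assume 30-day mortality of 10% in admitted controls and 13% to 15% in the intervention arm. The excess is 1,419 × 0.03 = 43 deaths up to 1,419 × 0.05 = 71 deaths. None enters PRV-2. With PRV-2 at 25% in both arms, the rule is met 2.5% of the time, its false-positive rate. The same holds for any size of excess.

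**3. Extra discharges.** Assume the intervention arm discharges 40%: 0.40 × 2,027 = 811 patients, 203 more than in controls. Give the usual 608 a 25% rate and the extra 203 a rate m. Then pI = (608 × 0.25 + 203 × m)/811, and pI − 0.25 = (203/811)(m − 0.25). The sign depends only on whether m exceeds 25%.

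| m | PRV-2, intervention arm | P(rule met) |
|---|---|---|
| 15% | 22.5% | about 0.1% |
| 25% | 25.0% | 2.5% |
| 40% | 28.8% | 35% |
| 50% | 31.3% | 74% |
| 60% | 33.8% | 95% |

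The rule thus compares the extra discharges with the usual discharged patients. The question for safety is how those same patients would have fared if admitted, and their control counterparts are not in PRV-2. If they do worse at home than they would have done in hospital, but still no worse than 25%, the rule stays silent.

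**4. What all-randomised 30-day mortality would add.** Assumed 10% in controls:

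| Intervention arm | 2,027 per arm | 1,013 per arm (half) |
|---|---|---|
| 12.5% | 71% | 43% |
| 13% | 85% | 56% |

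The baseline matters: for a 2.5-point rise at full size, power is 91% from a 5% baseline and 58% from 15%.

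**5. What it would lose if it replaced PRV-2.** Suppose mortality in the extra 203 discharges rises from an assumed 2% to 6%. Overall mortality moves by 203 × 0.04/2,027 = 0.4 points, from 10.0% to 10.4%, and the mortality signal is met about 6% of the time at full size. A rise from 2% to 12% moves it by 1.0 point and gives about 18%. Harm confined to the discharged group is diluted.

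**The case against.** A reader might infer that the rule cannot fire on harm from discharging more patients. The documents do not support that. Those patients enter PRV-2, and their revisits, hospitalisations and deaths count; the table in step 3 shows the rule responding once the rate among the discharged rises.

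A reader might also multiply the discharge share by the event rate (0.30 × 25 = 7.5 per 100 randomised against 0.40 × 25 = 10.0) and read the increase as harm. It is not evidence of harm. It counts events after direct discharge only, so the matching control patients, who were admitted, score zero by construction. The count rises with discharges even if nobody fares worse, and avoiding low-risk admissions is a stated aim (Hypothesis, item 3).

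Other points for the plan carry some weight. PRV-2 looks where the discharge proposal acts, and step 5 shows that replacing it would lose sensitivity there. The documents describe no mechanism for excess deaths confined to admitted patients, so step 2 shows what the rule can detect and does not forecast harm. Mortality in all patients and the percentage discharged are among the study's outcomes.

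Three defences do not close the gap. The word *main* leaves room for further rules, but none is given. The promised SAP is assigned analysis populations, statistical analysis and missing data, not termination, and is due only before database closure. PRV-1 covers everyone, but one-year status is collected in months 31 and 32, after inclusion ends in month 18.

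**Conclusion.** The point holds in limited form. The only stated rule leaves out about 70% of randomised patients, including every death during an index admission. It can miss harm from extra discharges when the event rate among those discharged does not rise. It can still be met when extra discharges raise that rate. The exclusion follows from the definitions and from the plan's 30% discharge share. The probabilities rest on the assumed discharge shares, event rates and mortality, and on a single look; earlier looks would have less power. Nothing here shows that the tool causes harm or that PRV-2 is useless as a safety signal. It is a cheap improvement to patient protection.

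**What to change.** Keep PRV-2 in the termination rule. Add, with equal standing, 30-day all-cause mortality from the index ED visit in all randomised patients, compared by assigned arm. Have the independent group see the proportion discharged in each arm next to PRV-2, so that a shift in the denominator is visible.

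The cost is one sentence in the protocol and matching text in the group's charter; the data are already collected. The downsides are that two signals make a false stop slightly more likely and call for judgement when they disagree, and that the mortality signal is weak at early looks (step 4).

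The change protects patients still being enrolled only if the group looks during enrolment. The Work Plan lists no 30-day analysis of Study 3 before months 19 to 24, after inclusion ends. That timing is a separate matter, but should be settled in the same text.
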